6.3 Secondary Endpoints

No sensitivity to percussion

No color change

No sensitivity to periapical palpation

No prolonged response to hot or cold

6.4 Study Overview

To confirm or reject the hypotheses a prospective, double-blind, randomized controlled trial (RCT) is designed to investigate the clinical performance of resin-infiltration as early caries management in a caries-prone population.

This CIP describes a three-year longitudinal, prospective, randomized controlled trial in split mouth design. The study includes a clinical team involving one on-site Principal Investigator (Site-PI)/operator and one back-up Clinical Investigator (CI)/operator.

The clinical site will enroll 150 subjects (in the age range of 14 years or older) with 2 study lesions. If the lesion management provided in the study appears to be insufficient within the investigated period, the study will provide a maximum of 2 traditional restorations for free to participants. The patients will be evaluated at six time points over a period of 3 years. Lesion status and caries risk will be monitored at 6-month intervals, while radiographic evaluation will be conducted at 12-month intervals at 1-, 2- and 3-year recall visits.

7 Design of the Clinical Investigation

The study will be designed as a controlled, double blind, randomized, prospective trial with a three year follow-up period regarding to CONSORT²² recommendations as a single-center study to investigate the effect of caries infiltration as an alternative treatment option.

7.1 Clinical Investigation Protocol

Study enrolment phase includes patient interviews, dental screening and bite-wing radiographs taking.

7.2 Participant Selection

Subjects recruited for this investigation will be selected from patients attending the clinical research area and recruited from advertisements (Attached). 150 patients aged 14 years and older will be recruited into the study to provide 150 resin infiltrated and control (no Treatment) lesions.

7.2.1 Inclusion Criteria

To be considered appropriate for inclusion in the study a patient must:

- Be age 14 years and older
- Have at least two vital carious teeth with caries ranging from enamel to just into dentin.
 - If the lesion is not on a 3rd molar
 - If the lesion is not developmental.
 - If the lesion is not cavitated
- Be a regular dental attendee able to return for assessments
- Be in good medical health and able to tolerate the dental procedure
- Have no chronic periodontitis which could compromise tooth retention.
- Have normal salivary function.
- Have normal bone levels
- No lingering cold sensitivity
- No periapical sensitivity
- No sensitivity to percussion

7.2.2 Exclusion Criteria

Patients will be excluded from participating in the study if:

- Do not meet the inclusion criteria
- Are not able to tolerate the time required for the study
- There is a history of an adverse reaction to any materials used in the study
- They are irregular dental attendees
- They maintain an unacceptable standard of oral hygiene.
- They have chronic periodontitis
- There is severe salivary gland dysfunction or reduced salivary flow is observed
- They are unable to return for recall appointments

8 Clinical Evaluations

At the screening visit and at each yearly recall a clinical evaluation will be conducted. The patient will be interviewed and receive a clinical examination. Additionally, at the screening and at annual visits a bitewing radiograph will be taken. The data of each visit is documented in the respective clinical report forms (Appendix 1). The criteria and codes used on the forms are documented in the protocol.

8.1 Baseline Records (*Radiographs*)

This section was revised and specified in Amendment 1 valid as of 30.11.2015!

Additional radiographs will not be taken for purpose of the trial only. The policy described below reflects the widely accepted, current best practice regarding detection, diagnosis and monitoring of approximal lesions. Standardized diagnostic bitewing radiographs will be taken using a standardized position device (DMG, Hamburg, Germany). The device facilitates optimal direction of the x-ray beam and thus leads to optimal diagnostic representation of the caries lesion.

Radiographic evaluation of the lesions and the quality of the adjacent enamel contact surface by standardized bitewing radiographs at baseline will be used to detect and diagnose the caries and monitor lesion change. An extensive review of the scientific evidence supports the importance of initial bitewings and radiographic recall examinations for description of caries progression.⁹⁻¹³ Both, the guidelines by Pitts and Kidd⁴ widely used in Europe, and the ADA/FDA-coordinated guidelines¹⁴ advise that in high risk children (age 10-16) the interval should be 6-12 month. The proposed timing of bitewings in our study (screening and at yearly intervals) falls well within these guidelines. They rather represent a minimum of the advised frequency for a caries-prone study population of young adults in the age range of 14+ years.

Quantification of caries lesions is greatly facilitated by digital processing of the radiographs.¹⁵ The advantage of using digital images is that electronic contrast enhancement may aid in visualization of the complex image.¹⁶ Recently, subtraction radiography was reported to be more accurate and reproducible for detecting mineral loss than subjective comparison of paired digital images.¹⁷ A digital subtraction program will be used to detect the differences in extent and density of the lesion. These programs have been successfully used to detect simulated and clinical caries progression.¹⁷⁻¹⁹

8.2 Clinic visits

Table 8.2 Overview of the procedures during each visit

Procedure	Preoperative	Baseline and Intervention	6 month Follow-up	12 month Follow-up	24 month Follow-up	36 month Follow-up
Time	D-1	D-0	M 6	M 12	M 24	M 36
Patient information		X				
Oral examination	X	X	X	X	X	X
Informed consent	X					
Medical history	X					
Inclusion and exclusion criteria	X					
Selection of eligible lesions		X				
Caries risk assessment	X					
Hot-cold sensitivity assessment	X	X	X	X	X	X
Dental examination	X	X	X	X	X	X
Radiographic examination		X		X	X	X
Assessment of lesion activity						
Randomization		X				
Intervention (Infiltration)		X				
Photographic documentation of lesions	X	X	X	X	X	X
Record of adverse effects			X	X	X	X
Instruction for oral health care		X	X	X	X	X
Color match		X	X	X	X	X
Discoloration		X	X	X	X	X
Surface Integrity		X	X	X	X	X
Secondary Caries		X	X	X	X	X

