9.5 Follow-up Evaluations

At each recall (baseline, 6-month, one, two and three years) all lesions will be assessed according to the asked criteria. In addition to the clinical and radiographic assessment (see below), each evaluation will include an evaluation of surface roughness, color match, post-operative sensitivity/discomfort, and presence or absence of secondary caries. Every attempt will be made to schedule the six month, one and two year recalls within ± 2 weeks of the recall interval. When assessors differ, a consensus will be reached before the patient is dismissed. In the event an Icon resin is unsatisfactory, details of the mode of failure will be documented and the necessary replacement / repair made.

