14.2 Withdrawal / Dropout of Subjects

Table 14.2 Withdrawal and drop-out of subjects separated by level, reason consequences

Level	Cause	Consequence
Lesion	An allocated lesion progresses radiographically into the middle or inner 1/3 of dentin (scores 4 and 5).	The lesion is treated invasively by removing the caries and placing a filling. The case is scored as "progressed" and "failure".
	The patient shows signs of reversible or irreversible pulpitis in an allocated tooth.	The tooth is treated. The case is scored as "progressed" and "failure".
Patient	The patient shows adverse reactions for one of the study materials.	Counteractive measures are taken. Unwanted effects are documented in CRF and CEF. The patient is scored as "drop out".
	The patient cannot be examined (i.e. x-ray during pregnancy)	The patient is scored as "drop out".
	One or more allocated lesions have been treated by an external dentist.	The patient is scored as "drop out".
	The patient cannot be contacted to make appointments.	The patient is scored as "drop out".
	The patient decides to withdraw his informed consent or study participation.	The patient is scored as "drop out".
Study	One or more patient(s) show severe unwanted side effects to treatment.	Individual counteractive measures are taken. The study is halted.
	More than four patients show unwanted side effects to one treatment or material used.	Individual counteractive measures are taken. The study is halted.

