18.1 Adverse Events

An adverse event (AE) is defined as any unintended adverse experience associated with the study materials or study procedures that results in an unplanned medical assessment or treatment, or changes the risk to subjects. Any adverse reaction to the treatment provided as part of the study will be fully investigated and reported to the IRB. AEs will be reported according to the IRB defined timelines using appropriate forms.

All materials and devices used in this study have been approved by local regulatory bodies and are currently on the market in various parts of the world. Their clinical use is according to label. Therefore, no foreseeable adverse events are expected.

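### No adverse-effect record is scheduled at the treatment visit or for six months after it, so mild or unvolunteered acute effects may be missed, misdated or not attributable to one tooth or material

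*Combined protocol and SAP*

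**What the plan says.** **Schedule (Table 8.2).** The row that begins "Intervention (Infiltration" has one mark, at D-0. The row "Record of adverse effects" has four, at M6, M12, M24 and M36; its D-0 cell is empty. Color match, discoloration, surface integrity and secondary caries are all marked at D-0, so that column is not confined to pre-treatment items.

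**Follow-up (section 9.5).** "At each recall (baseline, 6-month, one, two and three years) all lesions will be assessed according to the asked criteria". The section adds that "each evaluation will include an evaluation of surface roughness, color match, post-operative sensitivity/discomfort, and presence or absence of secondary caries". Later exposure is possible but unscheduled: "In the event an Icon resin is unsatisfactory, details of the mode of failure will be documented and the necessary replacement / repair made".

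**Definition (section 18.1).** An adverse event is "any unintended adverse experience associated with the study materials or study procedures". The definition then adds a condition, so that an experience counts only when it "results in an unplanned medical assessment or treatment, or changes the risk to subjects". The same section also says, without that restriction, that any adverse reaction to study treatment is investigated and goes to the IRB.

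**Consequences (Table 14.2).** A patient with an adverse reaction to a study material is scored as a drop-out, and unwanted effects are written into the study forms. The study is halted for a severe side effect in one or more patients, or when "More than four patients show unwanted side effects to one treatment or material used". No visit, time window or review frequency is attached to either halt rule.

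**The concern.** Reactions to a procedure done once are most likely on the day of the procedure and shortly after. The one adverse effect named in the risk section (5.2) is allergy to methylmethacrylate, which is a contact reaction. Yet no form is scheduled to ask about adverse effects at the visit where contact occurs, and the first scheduled question comes six months later.

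Three things are at stake:

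- **Capture and dating.** A mild effect that has resolved may be forgotten or misdated by month 6.
- **Attribution.** Each patient receives both Icon and placebo under blinding (sections 9.3 and 11.4.2), and the Table 14.2 count is per treatment or material. Recall after six months is a weak basis for assigning a transient effect to one tooth.
- **Use in the rules.** Drop-out status and the halt count both depend on which effects are known. Scheduled monitoring is not an early backstop, because the first annual visit comes 12 months after the study opens (section 12.1).

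**Working it through.** The plan gives no figure for this point, so there is none to reproduce. The check is a reading of the sections against each other, followed by an illustration of scale.

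**Reading**

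1. Scheduled exposures: one, at D-0. Scheduled adverse-effect records at D-0: none. Next scheduled record: M6. Visits in between: none.
2. Section 9.5 counts baseline among its evaluations and includes post-operative sensitivity or discomfort in each. The text therefore expects a tolerability check at D-0, while the adverse-effect row of Table 8.2 leaves D-0 empty.
3. Section 18.1 requires an unplanned assessment or treatment, or a change in risk, before something is an *adverse event*. It then speaks of any *adverse reaction*. Table 14.2 uses *adverse reactions* for drop-out and *unwanted side effects* for the halt. These terms are not related to each other. A mild acute effect could fall outside the first and still count under the last.

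**Size of a six-month lag**

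Inputs: 150 patients (section 6.4) and a gap of 6 months (Table 8.2). Assumption: even accrual over A months. Patients treated during the gap = min(150, 150 × 6/A).

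- A = 6: 150 × 6/6 = 150
- A = 12: 150 × 6/12 = 75
- A = 18: 150 × 6/18 = 50
- A = 24: 150 × 6/24 = 37.5, about 38

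These are upper values. They apply if nothing is known before M6, and they shrink if the event falls late in accrual.

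**Would the count be reached at all?**

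More than four means the fifth patient. With X binomial (n = 150, event rate p), P(X ≥ 5) is 1.8% at p = 1%, 18% at 2%, 87% at 5% and 99.9% at 10%. The documents give no rate, so these values of p are assumptions.

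**When would the fifth case be known?**

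This was simulated with 20,000 runs per setting. Accrual is even, events occur at D-0, and a share of them is known at once with the rest known at M6. The entries are the median number of patients already treated when the fifth case is known.

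| Accrual | Event rate | All known at once | Half | None before M6 |
|---|---|---|---|---|
| 6 months | 5% | 87 | 150 | 150 |
| 6 months | 10% | 47 | 94 | 150 |
| 12 months | 5% | 87 | 124 | 150 |
| 12 months | 10% | 47 | 84 | 122 |
| 18 months | 5% | 87 | 112 | 137 |
| 18 months | 10% | 47 | 72 | 97 |
| 24 months | 5% | 87 | 105 | 124 |
| 24 months | 10% | 47 | 66 | 84 |

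The 5% rows are medians among the runs that reach five cases (about 87% to 88% of runs). The last column agrees with the simple formula: at 12 months and 10%, 47 + 75 = 122. At 12 months and 5%, 87 + 75 = 162, which is capped at 150.

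**The case against.** The strongest answer is that Table 8.2 is not the only route for adverse effects. Section 18.1 sends any adverse reaction to the IRB on the IRB's timelines, section 18.2 gives an emergency contact for serious events, section 18.3 has the investigator report to the sponsor on a dedicated form, and Table 14.2 has unwanted effects documented. None of these waits for a visit. The operator is present on D-0, so a visible reaction in the chair is covered at once. Section 9.5 adds a sensitivity and discomfort check at baseline, and Table 8.2 marks hot-cold sensitivity there. The case report form and the material application form were not available for review and the adverse event form is redacted, so a D-0 item may already exist.

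Most of this stands, and it rules out two stronger readings. A reader might infer that acute reactions are in fact under-recorded; the documents support only a risk of that, for effects that are mild or that nobody volunteers. A reader might also infer that the halt count must run six months late, or that all 150 patients would be treated first. The halt rules are not tied to Table 8.2, one severe case is enough by itself, and the figure of 150 needs both a 6-month accrual and no event known before M6.

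What does not fall away is that event-driven reporting depends on someone noticing and volunteering an effect. The section 9.5 check covers one type of symptom, and it disagrees with the empty D-0 cell.

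**Conclusion.** The point holds as a minor gap in the schedule. The plan as written has no scheduled general adverse-effect record at its only scheduled exposure or in the six months after it. The exposed group is patients with mild or unvolunteered acute effects.

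The size cannot be fixed. The accrual dates are redacted, and the documents give neither an acute event rate nor the share of events that would be reported spontaneously. Under the assumptions shown, the lag in the halt count runs from nothing (all events known at once) to about 38 to 150 further treated patients (none known before M6, accrual over 24 down to 6 months). At a 1% event rate the count would seldom be reached at all.

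D-0 is the only scheduled exposure, not the only possible one, since section 9.5 allows later repair or replacement. The primary efficacy comparison is affected only to the extent that an adverse reaction turns a patient into a drop-out under Table 14.2.

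**What to change.** Mark "Record of adverse effects" at D-0 in Table 8.2, to be completed by tooth after the procedure and before the patient leaves. Keep the M6 to M36 records.

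Separately, reconcile sections 8.2, 9.5, 14.2 and 18.1 on two matters: when adverse effects are recorded, and how *adverse event*, *adverse reaction* and *unwanted side effects* relate to each other in the drop-out and halt rules. What those rules should be is for the sponsor and the investigator to settle; the request is only that the sections agree.

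**Cost.** One line on the case report form at a visit that already takes place, and a few more minor events reported. Because the terms in Table 14.2 are undefined, asking directly could also bring more patients within the drop-out or halt wording, so the reconciliation should come before the new records are used.

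**Limits.** Effects that begin after the patient leaves still rely on event-driven reporting. A reaction that is not local to one tooth cannot be assigned to a material by this record.

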8.3 Evaluation Categories

Following is a description of the different evaluation categories that will be used to determine caries risk status, to monitor the lesions and to determine the primary and secondary endpoints of this investigation.

8.3.1 History Taking (Interview)

- Oral Health care behavior

8.3.2 Diet

- Snacking: frequency and content
- Softdrinks: frequency and sipping

8.3.3 Local Ecology

- salivary function
- bone levels
- cold sensitivity
- periapical sensitivity
- sensitivity to percussion

8.3.4 Caries Experience

- DMFT/ WHO Standard

8.3.5 Individually standardized record (Radiographs)

- DMG criteria for Icon treatment

8.4 Evaluation Criteria

8.4.1 Pre-Ambule

To avoid confusion due to multi-continental data sharing the European form for dates is provided (dd/mm/yyyy).

8.4.2 Inclusion Criteria

In order to be eligible for the study, each participant must meet preliminary eligibility criteria and the participant or the guardian must be willing to sign a statement of informed consent. This will document the agreement of the participant to participate in the study activities. The patient must have two lesions which meet criteria as listed in Table 8.4.2, shown below.

Additionally, participants will be asked by study personnel not to participate in any other therapeutic research studies during the participant's follow-up period from baseline to the 36 month visit.

Table 8.4.2. Criteria used in the radiograph examination

E1	Radiolucency confined to the outer half of enamel
E2	Radiolucency involving the inner half of enamel
D1	Radiolucency in the outer third of dentin
D2	Radiolucency in the middle third of dentin
D3	Radiolucency in the inner third of dentin
D4	Tooth must have proximal contact
D5	Patient must be able to tolerate procedure (ie – Jaw-opening must be adequate)
D6	Tooth must have adequate attachment
D7	Tooth must be vital and not sensitive to palpation or percussion
D8	Tooth to be restored must occlude with an articulating surface
D9	Tooth must not be fractured or otherwise "non-restorable"

[figure not shown]

Figure 3: DMG criteria for treatment planning for Icon infiltration therapy. Adopted from DMG, Hamburg, Germany.

8.4.3 Local ecology

Sensitivity (Cold response/Biting response)

Sensitivity will be measured using a visual analogue scale.

Preoperatively –Cold response on the selected carious tooth will be measured by applying a cotton pellet soaked in Endo Ice to the tooth for 3 seconds and asking the subject to place an X on a 10 cm line labeled 1 on the left and 10 on the right. They will be told that 10 represents the worst pain they can imagine (childbirth, major surgery or kidney stones) and 1 represents no sensation at all. Stimuli – biting pressure (biting on a cotton tip applicator) and cold tests will be measured using the same scale.

Saliva function

Saliva function will use stimulated saliva flow measurement. Patient will chew paraffin for 2 minutes, hold saliva in their mouth, and then expectorate into a graduated cylinder. Amount of saliva flow will be expressed as ml.

DMFT Score

Teeth will be scored as D = decayed, M = missing, F = filled and T = teeth and the final DMFT value will be calculated as recently described.³⁷

9 Clinical Measurements and Procedures

9.1 Screening Visit

The screening phase allows confirmation of subject eligibility for the trial based on inclusion and exclusion criteria. Screening includes patient information, eligible lesion are evaluated by a study investigator and randomly selection of caries lesions for treatment.

9.2 Selection of Lesions (Screening visit only)

After allowing each subject an opportunity to read and consider the consent form and answering any questions concerning the study, each subject will be asked to complete and sign the consent form. Appropriate vitality and radiographic assessments will be completed and any pathology noted and recorded. A radiograph will be made of each carious tooth lesion to be included in the study. The depth of the carious lesions will be measured and recorded (E1-2 or D1). Periapical lesions will be recorded. Digital images of the tooth will be made and filed. Cold and hot response will be recorded and the time after the stimulus is applied for any pain to stop will be recorded. Patient age and tooth number will be recorded.

9.3 Randomization

A random assignment of the treatment to teeth is based on equal distribution of the two treatments; each subject will receive both a placebo controlled or an Icon resin treatment for the two proximal carious teeth, assigned by beginning with the tooth with the lowest number, the specific procedure applied to each tooth will be determined by selecting from a box containing two choices (A or B) by the clinician doing the procedure. One tooth (the one with the lowest tooth number in the universal numbering system) will receive the treatment drawn from a box containing the names placebo or Icon. The universal numbering system begins with #1 - the maxillary right third molar and proceeds to #16 the maxillary left molar. In this system the mandibular left third molar is # 17 and the mandibular right third molar is tooth number #32. The treatment (the first one drawn) will be placed on the tooth with the lowest number. The remaining tooth will receive the second treatment. Clinicians and patients

receiving the two treatments will be blinded as to the treatment applied to the specific tooth.

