9.4 Intervention Visit

9.4.1 Intervention Site “TREATMENT”

During the screening examination and after informed consent has been obtained from the subject, bite wing radiographs will be made using a customized holder for the digital sensor using VPS impression material. The subject position will be controlled in 3 dimensions by placing holders in the subject's ears and placing their chin in a holder. The positions used for the initial set of radiographs will be recorded and used for all subsequent x rays to standardize their position at each recall. At a separate appointment, each selected subject will be instructed in oral hygiene procedures to include brushing, flossing and the use of a fluoride containing toothpaste. To be included in this study the subject must have two teeth with similar sized lesions. After the lesions are selected, one of two treatments will be selected from a box by the clinician doing the procedure. One of the “treatment tooth” will randomly receive the infiltrating resin (Icon). Teeth will be isolated with a rubber dam, the tooth surface cleaned with non-fluoride prophylactic paste and pumice. The Icon material will be applied following the manufacturer's instructions and light cured with S 10 curing light (3M ESPE, St Paul, MN). Output from the curing light will be measured and recorded weekly. The Icon infiltrating resin will be polished using interproximal finishing/polishing strips (Sof Lex, 3M ESPE, St Paul, MN). Subjects will be given a letter to take to their local dentist asking them not to treat the selected lesions without informing the investigator first. Subjects will be recalled at 6, 12, 24 and 36 month intervals and at radiographs will be made of the control and test lesions after 12, 24 and 36 month . During all visits, oral hygiene will be reinforced.

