9.4.2 Intervention Site “CONTROL”

During the screening examination and after informed consent has been obtained from the subject, bite wing radiographs will be made using a customized holder for the digital sensor using VPS impression material. The subject position will be controlled in 3 dimensions by placing holders in the subject's ears and placing their chin in a holder. The positions on the initial set of radiographs will be recorded and used for all subsequent x rays to standardize their position at each recall. At a separate appointment, each selected subject will be instructed in oral hygiene procedures to include brushing,

flossing and the use of a fluoride containing toothpaste. To be included in this study the subject must have two teeth with similar sized lesions. After the lesions are selected, one of two treatments will be selected from a box by the clinician doing the procedure. One tooth will randomly receive the infiltrating resin (Icon) while the other will receive a placebo. Teeth will be isolated with a rubber dam, the tooth surface cleaned with non-fluoride prophylactic paste and pumice. Syringes identical to the Icon materials will be supplied by DMG for the placebo procedure. The syringes will be filled with the solutions having the same consistency and color as the Icon material. The placebo material will be applied following the manufacturer's instructions and light cured with an S 10 curing light (3M ESPE, St Paul, MN). Output from the curing light will be measured and recorded weekly. The placebo material and the Icon infiltrating resin will be polished using interproximal finishing/polishing strips (Sof Lex, 3M ESPE, St Paul, MN). Subjects will be given a letter to take to their local dentist asking them not to treat the selected lesions without informing the investigator first. Subjects will be recalled at 6, 12, 24 and 36 month intervals and at each recall radiographs will be made of the control and test lesions. During these visits, oral hygiene will be reinforced.

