11.3 Evaluation Strategy

Four trained operators will complete the direct and indirect evaluations of the carious teeth and seal the carious lesions. Two trained and calibrated examiners will complete the evaluation process at each recall. The PI will select all lesions for this study.

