14.3 Length of follow-up – Potential Study Extension

Based on the actual study design there is no extension planned. If obtained data indicate a necessity for follow-up investigations this issue will be discussed with the sponsor and documented in the study files.

15 Confirmation of Study Material Application

Application of study material will be documented in the Study Material Application form (Appendix A2) including patient ID, investigator, date of application, material batch number and signature.

16 Ethical Considerations

This protocol was approved by the IRB from the Federal University of Alabama (Appendix 3). Parents or guardians will sign an informed consent (Appendix 4). Operative dental treatment will be provided to the participants when necessary.

17 Relevant Standards and Guidelines

The Clinical Investigation Protocol for this study includes all components and documentation as required to conform to international standards for clinical research (CONSORT, ISO/DIN and Good Clinical Practice Guidelines).²⁰⁻²²

18 Adverse Events

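### The operator draws the allocation from a two-choice box after the lesions are chosen, with no concealed sequence or record of the draw described, and section 9.3 contradicts itself on whether the drawer sees the treatment name

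*Combined protocol and SAP*

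**What the plan says.** Section 9.3 of the protocol sets 1:1 allocation within each subject: "A random assignment of the treatment to teeth is based on equal distribution of the two treatments". The procedure for each tooth is "determined by selecting from a box containing two choices (A or B) by the clinician doing the procedure". The next sentence describes the same box differently: the lowest-numbered tooth is to "receive the treatment drawn from a box containing the names placebo or Icon". The link from draw to tooth is fixed: "The treatment (the first one drawn) will be placed on the tooth with the lowest number". The section ends by stating that clinicians and patients are blinded to which tooth received which treatment.

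Section 9.4.1 gives the order of events: "After the lesions are selected, one of two treatments will be selected from a box by the clinician doing the procedure". Section 9.4.2 repeats this for the control site and adds "To be included in this study the subject must have two teeth with similar sized lesions".

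Other relevant places:
- **Section 9.2:** lesion depth (E1-2 or D1) and tooth number are recorded when lesions are selected.
- **Section 11.3:** "The PI will select all lesions for this study". The same section gives four operators, and section 6.4 lists the PI as an operator.
- **Sections 9.4.2 and 11.4.2:** placebo and Icon come in matching syringes, with the same colour and consistency.
- **Section 15:** application is documented on the Appendix A2 form, "including patient ID, investigator, date of application, material batch number and signature".
- **Section 18.2:** a name-code list exists for unblinding.

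The SAP does not mention randomization.

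**The concern.** In a split-mouth trial the patient serves as their own control, so the main threat to the comparison is a systematic difference between the lesion that gets Icon and the one that does not. Random allocation is what rules this out. It does so only if the person assigning cannot foresee or revise the result.

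Here the operator makes the draw after the pair is known. Lesions need only be similar in size, a term the protocol does not define, and eligibility runs from enamel to just into dentin. Section 4.1 itself says that lesions which have reached inner enamel are hard to halt. The two teeth of a pair can therefore differ in prognosis. If the drawer can tell which draw means Icon, an unwelcome result can be drawn again, and nothing described in the plan would show it.

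**Working it through.** The plan states no figure on this point, so the main check sets its passages side by side. The arithmetic only shows how a bias would scale.

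**Step 1. Can the drawer aim the draw?** This depends on what the box holds.
- *Treatment names.* The operator reads the assignment at the draw. This is incompatible with the blinding statements in 9.3 and 11.4.2, and a repeated draw could be aimed at either tooth.
- *A/B codes with matched syringes.* The operator does not know which code is Icon, so a repeated draw cannot be aimed. The exception is one A/B code fixed for all patients: once it is known, for example after a single unblinding under 18.2, every later draw is readable. The text does not say whether the code varies by patient.

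Section 9.3 supports both readings.

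**Step 2. Would a repeated draw be visible?**
- The lowest-numbered-tooth rule fixes where the first draw goes. It does not show how many draws were made.
- The tooth and depth records in 9.2 fix the pair, not the draw.
- The name-code list (18.2), the batch number (15) and the test/control image code (11.4.3) may show what was finally applied. With no list made in advance, there is nothing to reconcile them against.
- The fields named for the Appendix A2 form do not include the tooth or the draw.

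**Step 3. How would bias scale?** Let f be the share of draws steered so that Icon goes to the lower-risk tooth, and g the within-pair risk gap. Unsteered pairs contribute zero on average and steered pairs contribute g, so

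bias in the risk difference = f × g.

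Write f = u × s, where u is the share of pairs with a real gap and s the share of those steered. All values are assumptions:
- Low: 0.3 × 0.1 × 0.2 = 0.006, or 0.6 points.
- Middle: 0.5 × 0.2 × 0.3 = 0.03, or 3 points.
- High: 0.5 × 0.3 × 0.4 = 0.06, or 6 points.

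In this range f runs from 0.3 × 0.1 = 0.03 to 0.5 × 0.3 = 0.15.

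**Step 4. Effect on a test.** Section 11.2 gives 150 × (1 − 0.20) = 120 pairs at three years. A simulation used 120 pairs, no treatment effect, mean risk 50%, lesions independent given their risks, a two-sided exact McNemar test at 0.05, and 10,000 runs. It gave these false-positive rates (bias in points in brackets):

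| g | f = 0 | f = 0.10 | f = 0.25 | f = 0.50 |
|---|---|---|---|---|
| 0.10 | 3.8% | 3.9% (1) | 5.0% (2.5) | 9.6% (5) |
| 0.20 | 4.2% | 4.2% (2) | 9.0% (5) | 29.1% (10) |
| 0.30 | 3.9% | 6.2% (3) | 17.3% (7.5) | 57.1% (15) |

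Occasional steering changes little; frequent steering on unequal pairs changes a great deal. The SAP names McNemar's test for the depth outcome and Fisher's exact test for the primary filling outcome, so the table is not a calculation for the primary analysis.

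**The case against.** A reader might infer that allocation can be steered whatever the box contains, that it would leave no trace, and that the trial cannot be audited. The documents do not support that.

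- Aimed steering requires knowing what the draw means. With A/B codes, identical syringes and the stated blinding, the operator does not know. The existence of a name-code list favours this reading. This objection stands, and it confines the direct risk to the named reading.
- Absence of a trace is not established. The Appendix A2 fields are introduced as inclusions, not as a complete list, and the forms and both amendments cannot be read in the available copy. What can be said is that no record of the draw is described in the available text.
- The draw is not the only safeguard. The tooth-number rule, the requirement for lesions of similar size, and the recording of tooth and depth at selection all limit what an operator could do. This stands too, although none of them would reveal a second draw.
- The person who selects lesions may not be the one who draws: the PI selects and four operators treat. The overlap is possible, not certain.
- The sizes are assumed. Six points is small beside the 37.8-point difference that the SAP cites, but that difference concerns progression. The documents give no expected filling rate to compare with for the primary outcome.
- It is also tempting to show one reversed pair overturning a result: with 10 discordant pairs, exact McNemar p moves from 0.021 (9 to 1) to 0.109 (8 to 2). Nothing in the plan leads to 10. A 37.8-point difference over 120 pairs needs at least 0.378 × 120 = 45.4, so 46, discordant pairs.

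**Conclusion.** The point holds in a limited form. The plan describes a chairside draw by the operator after the lesions are chosen, and the available text gives no advance sequence, no concealment and no record of the draw. Its description of the box contradicts itself. If the box holds names, blinding of the operator fails and a draw could be repeated or steered. If it holds codes, the risk depends on one fixed code serving all patients and becoming known.

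Nothing in the documents suggests that any draw was or would be steered, and no size can be derived from them. The range of 0.6 to 6 points rests wholly on assumed values of u, s and g. The weakness is that the described procedure neither prevents a repeated draw nor provides a means of detecting one, while a better method costs very little. It should be changed, but it does not by itself undermine the design.

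**What to change.** Replace the box in 9.3, 9.4.1 and 9.4.2 as follows.

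1. Generate by computer, before enrolment, a list of 150 assignments for the lower-numbered tooth; the other tooth receives the alternative. Someone who neither treats nor assesses patients prepares and holds the list.
2. Issue the assignments as patient-numbered kits, each with two syringe sets marked only *lower-numbered tooth* and *higher-numbered tooth*. The kits carry no treatment name and no fixed A/B code.
3. Open a kit only after both tooth numbers and depth codes are in the CRF. Section 9.1 places a random selection at screening, while Table 8.2 places randomization at the intervention visit; state one time for allocation.
4. Record kit number, tooth and date on the Appendix A2 form, and reconcile the forms against the list.
5. Delete from 9.3 the statement that the box holds treatment names.

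The cost is kit labelling and a short amendment. No patients, visits or procedures are added.
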